## Specimen Management Committee

A Specimen Management team will decide priority and allocation of samples not included in the original plan. The team will consist of the Overall study PI, and the Site PIs and Chairmen of the Pathology, Radiation Oncology, ENT, and Medical Oncology for the study and for the teams at each site.. Proposals will be reviewed and upon a majority agreement, samples will be allocated for each study. A quorum for decisions would include at least one member from each site and one of the study chairmen of Radiation Oncology, Otolaryngology, Pathology, and Medical Oncology.

## 10.0 STUDY CALENDAR (History, Exam and Lab)

	Pre-Study 	Post Surgery Surveillance Follow up	During Chemo/RT, groups 2,3	Post CRT Follow up (± 1 month)
Informed Consent	To be obtained before enrollment			
Medical History	Within 10 days before registration	Every Visit	Per SOC at all clinical visits	Every Visit
Smoking History	Within 10 days before registration			
Concurrent meds	At Screening	Every Visit	Weekly	
Physical Exam^1	Within 10 days before registration	Every Visit	Per SOC at all clinical visits	
CBC/BMP	Within 10 days before registration	Preop and post-op and then no requirement for Groups I and II and per SOC for Group IIIA and IIIB	Preop and post-op and then no requirement for Groups I and II and per SOC for Group IIIA and IIIB	
Dysphagia Assessment Questionnaire	Within 10 days before registration	12, 24, 36 months (± 1 month)	Weekly	12, 24, 36 months
Adverse Event evaluation			Weekly	Each visit
B-HC (for WOCP)	Within 7 days before registration			

 Ht, Wt, Performance status, neurologic examination, vital signs (heart/blood pressure/temperature). Height is only collected at baseline/pre-study.

CONFIDENTIAL

This document is confidential. Do not disclose or use except as authorized.

Tumor Assessment						
	Pre-Study	Surgery	Pathological Evaluation	ChemoRT (if reassigned)	Reassessment (Week 8-10)	Surveillance ( $\pm$ 1 month)
Physical tumor Examination	Patients get an exam as part of their routine visits, same for TNM and will be done when the patient is seen and before they are consented	Intraoperative	Path Check List		X	
TNM Staging	patients get an exam as part of their routine visits, same for TNM and will be done when the patient is seen and before they are consented		Path Check List			
Nasopharyngoscopy					X	
Examination under anesthesia (EUA)	Within 8 weeks before registration if possible. (Does not need to be repeated if time period exceeds 8 weeks)	May be done if investigator deems it necessary				
PET/CT and/or high resolution CT or MRI of the neck (base of skull clavicles)	Within 28 days before registration			PET/CT or CT with contrast and examination At 12-16 weeks	PET/CT or CT with contrast and examination Refer to Section 5.0 "Treatment Plan" for the frequency in each group	

CONFIDENTIAL

This document is confidential. Do not disclose or use except as authorized.

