### **13.2 Procedures for AE and SAE Recording and Reporting**

Reporting: Participating investigators will assess the occurrence of AEs and SAEs at all participant evaluation time points during the study.

All AEs and SAEs whether reported by the participant, discovered during questioning, directly observed, or detected by physical examination, laboratory test or other means, will be recorded in the participant's medical record and on the appropriate study-specific case report forms.

The descriptions and grading scales found in the CTEP Active Version of the NCI Common Terminology Criteria for Adverse Events (CTCAE) will be utilized for AE reporting. The CTEP Active Version of the CTCAE is identified and located on the CTEP website at:

[http://ctep.cancer.gov/protocolDevelopment/electronic\\_applications/ctc.htm](http://ctep.cancer.gov/protocolDevelopment/electronic_applications/ctc.htm)

All appropriate treatment areas should have access to a copy of the CTEP Active Version of CTCAE.

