### **13.4 Reporting to the Study Center**

#### **13.4.1 Serious Adverse Event Reporting**

All serious adverse events that occur after the initial dose of study treatment, during treatment, or within 30 days of the last dose of treatment must be reported to the MSSM Overall Principal Investigator on the local institutional SAE form for the local IRB and electronically on the eRAP CRF. This includes events meeting the criteria outlined in Section 11.1.2, as well as the following:

- Grade 2 (moderate) and Grade 3 (severe) events that are unexpected and at least possibly related/associated with the intervention.
- All Grade 4 (life-threatening or disabling) events that are unexpected or not specifically listed in the protocol as not requiring reporting.

CONFIDENTIAL

This document is confidential. Do not disclose or use except as authorized.

- All Grade 5 (fatal) events while the participant is enrolled and actively participating in the trial OR when the event occurs within 30 days of the last study intervention.

Note: If the participant is in long term follow up, report the death at the time of continuing review.

Participating investigators must report each serious adverse event to the MSSM Overall Principal Investigator within 24 hours of learning of the occurrence by Fax and email. In the event that the participating investigator does not become aware of the serious adverse event immediately (e.g., participant sought treatment elsewhere), the participating investigator is to report the event within 24 hours after learning of it and document the time of his or her first awareness of the adverse event. Report serious adverse events by telephone, email or facsimile to:

[name] at Ph- [contact]    [[contact]](mailto:[contact])

Within the following 24-48 hours, the participating investigator must provide follow-up information on the serious adverse event. Follow-up information should describe whether the event has resolved or continues, if and how the event was treated, and whether the participant will continue or discontinue study participation.

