### 14.2 Safety Meetings

Because this is a Phase II trial an internal Data Safety Monitoring Board will be required to review and monitor toxicity, accrual data from this trial and interim results on this trial. The committee will be composed of [name] (Chair), [name], [name], [name] and the statistician. The

CONFIDENTIAL

This document is confidential. Do not disclose or use except as authorized.

Review group will meet quarterly to review survival and recurrence data from the trial. An independent MSSM statistician shall be a member. The chairman of the DSMB will prepare minutes and report to the DSMC. The study report will remain blinded for efficacy results unless there is sufficient reason for the DSMB to consider halting the trial.

The DSMB will meet semi-annually and/or more often if required to review toxicity and accrual data. Information to be provided to the committee may include: up-to-date participant accrual; all unexpected adverse events that have been reported; summary of all surgical complications or deaths while being treated and during active follow-up; any response information; audit results, and a summary provided by the study team. Other information (e.g. scans, laboratory values) will be provided upon request.

**Adverse Events.** safety data, including all protocol-defined and serious unanticipated adverse events, will be collected throughout the entire course of the study. Expedited reporting to the IRB and study sponsor will be required for any unexpected serious adverse event.

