#### **16.5 Analysis of Secondary Endpoints**

The secondary endpoint of overall survival will be analyzed using Kaplan-Meier curves and a log-rank test for the difference between the two therapy groups. Five year OAS, DFS and LRC will be calculated using a log-rank test will be used to test for differences between the two treatment groups.

Toxicity is another secondary endpoint. We will compute for each arm the toxicity rate and provide the corresponding 90% confidence intervals based on the exact binomial distribution.

Reporting and Exclusions

Not Applicable.

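### The study calendar leaves adverse-event evaluation blank in post-surgery surveillance, against Sections 13.2 and 14.2, and the per-arm toxicity rates in Section 16.5 have no common window to offset unequal ascertainment

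*Combined protocol and SAP*

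**What the plan says.** **Calendar (Section 10.0).** The row "Adverse Event evaluation" is empty before study and under "Post Surgery Surveillance Follow up". It is weekly under "During Chemo/RT, groups 2,3" and at each visit in the post-CRT column. In the same surveillance column, medical history, concurrent medications and physical exam are all required at every visit.

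**Text.** Section 13.2: "Participating investigators will assess the occurrence of AEs and SAEs at all participant evaluation time points during the study". Section 14.2: "safety data, including all protocol-defined and serious unanticipated adverse events, will be collected throughout the entire course of the study". Section 11.1.1 makes every operated participant evaluable for toxicity. Section 13.7 follows up adverse events from the start of the intervention and throughout the study. None of these excepts a group.

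**Forms (Section 14.1).** The adverse-event form is due 10 days after the last day of a cycle.

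**Analysis.** Section 16.5: "We will compute for each arm the toxicity rate", with a 90% exact binomial interval. It gives no assessment window, grade threshold or common schedule. Section 12.0 adds that adverse-event assessments will be used, with the questionnaires, to compare arms.

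**The concern.** The calendar and Section 13 give sites different instructions for the surveillance period. The form deadline makes this worse, because a patient treated by surgery alone has no cycle to trigger the form. A site that took its visit checklist from the calendar could see a Group I patient, take a history, examine the patient and record no adverse-event assessment.

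The direction matters. The background (Sections 2.2 and 2.3) argues that surgery alone spares patients the late morbidity of radiotherapy. Under-recording in Group I would push the reported toxicity rates towards that argument. Each arm's rate is a crude proportion with no stated window, so the analysis does nothing to limit the effect of groups being looked at with different frequency.

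**Working it through.** The plan states no toxicity rate and no toxicity-based sample size, so there is no figure to reproduce. The check is a count of scheduled evaluations, followed by an illustration.

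**1. Inputs.**
- Group I and Group II visits in year 1: every 3-4 months (Section 5.0), so 12/4 = 3 to 12/3 = 4.
- Group IIIA and IIIB visits in year 1: monthly (Section 5.0), about 12.
- Radiotherapy length at 5 fractions a week: Groups II and IIIA, 50/2.0 = 25 fractions, 25/5 = 5 weeks; Group IIIB, 56/2.0 = 28 fractions, 28/5 = 5.6, about 6 weeks.

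**2. Scheduled adverse-event evaluations in year 1** (weekly checks plus follow-up visits; the post-CRT column is taken to cover Group II).

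| Group | Calendar alone | With Section 13.2 applied |
|---|---|---|
| I | 0 | 3-4 |
| II | 5 + 3-4 = 8-9 | at least 8-9 |
| IIIA | 5 + 12 = 17 | at least 17 |
| IIIB | about 6 + 12 = 18 | at least 18 |

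These counts are approximate. If the monthly visits overlap the radiotherapy weeks, the Group III totals fall slightly.

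**3. What filling the cell achieves.** It removes the calendar zero. It does not equalise ascertainment: the ratio of irradiated to Group I evaluations still runs from 8/4 = 2 to 18/3 = 6.

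**4. How frequency could act on detection (assumption).** Suppose an event is recorded only if present at a visit, so that detection = min(1, duration / visit interval). For a 4-week event:
- weekly visits: 1.00
- monthly visits: 4/4.345 = 0.92
- visits every 3 months: 4/13.04 = 0.31
- visits every 4 months: 4/17.38 = 0.23

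For a 13-week event, visits every 3 to 4 months detect 1.00 to 0.75. Long-lasting toxicity is therefore much less sensitive to visit frequency than short-lived toxicity. Recall at visits and spontaneous reports would narrow all these gaps.

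**5. How detection could act on the reported rate (assumption).** Take a true rate of 30% and n = 100, the planned Group I size, with the 90% exact interval of Section 16.5:
- full detection: 30/100, 22.5% to 38.4%
- 50% detection: 15/100, 9.5% to 22.2%

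The two intervals do not overlap although the true rate is the same. The 30% and the detection probabilities are assumptions chosen to show the mechanism; they are not estimates for this trial.

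**The case against.** The strongest reply is that the protocol already covers this. Sections 11.1.1, 13.2, 13.7 and 14.2 reach every operated patient, Group I has scheduled visits, and Section 15.6 obliges sites to follow the protocol as written. That stands. A reader might infer from the blank cell that Group I has no adverse-event assessments; the documents do not support this, because the zero is a count from the calendar alone.

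The cell is also weak evidence by itself. The column names a period, not Group I, and its CBC/BMP entry addresses all groups, so the interval between surgery and radiotherapy in Groups II and III may be affected too. The post-CRT column has blanks for physical exam and concurrent medications that cannot be meant literally. Footnote 4 on the row has no visible text. It also marks concurrent medications, which are required at every surveillance visit, so an exemption is unlikely but not excluded. The conflict with Section 13.2 remains.

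A reader might go on to conclude that the per-arm rates are not comparable. That goes too far: Section 16.5 plans no between-arm toxicity test, weekly checks partly reflect a treatment exposure Group I lacks, and late function is measured by questionnaire in all groups on one schedule (Section 12.0). What stands is a risk of unequal ascertainment, which Section 12.0's stated intention to compare arms makes relevant.

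A reader might also see between-group bias in the serious-event rule of Section 13.4.1 ("within 30 days of the last dose of treatment must be reported"). That limit applies to all groups and concerns reporting to the study center, so it does not support such a claim.

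**Conclusion.** The concern holds as an internal inconsistency with a modest analytic consequence. The calendar's surveillance column contradicts Sections 13.2 and 14.2, and the form deadline does not fit patients without cycles. A site following the calendar could under-record Group I events. Even with Section 13.2 followed, year-1 evaluations are about 3-4 in Group I against about 8-18 in the irradiated groups, so crude per-arm rates without a common window risk favouring surgery alone.

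The size of that effect cannot be derived from the documents, which give neither toxicity rates nor detection probabilities. The conclusion assumes that the blank cell is not explained by a footnote that cannot be seen, and that some sites may use the calendar as their working checklist, which the protocol does not state. It should be fixed because the remedy is cheap.

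**What to change.** 1. **Section 10.0:** enter *Every visit* for adverse-event evaluation in the surveillance column, to agree with Section 13.2, and check that footnote 4 does not say otherwise.
2. **Section 14.1:** give the adverse-event form a visit-based deadline for patients who have no treatment cycles.
3. **Section 16.5:** report acute toxicity (surgical and adjuvant-phase) separately from late toxicity (grade 3 or worse, and feeding-tube use). Assess late toxicity in all groups at the existing 12-, 24- and 36-month visits, and rest any between-group comparison on the late rates.

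The third change is needed because the first does not equalise frequency; assessing all groups at the same late visits does. Both follow-up columns already carry assessments at 12, 24 and 36 months, and the EORTC QLQ-H&N35 already asks about feeding-tube use, so no new visit or instrument is required. The cost is one calendar cell, a line in the submission table, a few sentences in Section 16.5, slightly more adverse-event data entry and one more results table.

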### CORRELATIVE STUDIES CALENDAR (See Section 16.0 for QOL)

	Pre-Study			Post-Study Follow-up (± 1 month)
Tissue Microarray	X			
CTC's (cell Save tube)	X			
T Cell Specificity and Function	X			12, and 24 months
Serologic Assessments	X			6, 12, 24 and 36 months

CONFIDENTIAL

This document is confidential. Do not disclose or use except as authorized.

## 11.0 MEASUREMENT OF EFFECT

### 11.1.1 Definitions

Evaluable for toxicity. All participants who go on to surgery will be evaluable for toxicity from the time of their first treatment. Patients who are screened will be evaluated and the reason for screen failure will be recorded

Evaluable for Primary Outcome: Only patients who are entered and have surgery will be eligible for assessment of the primary outcomes (LRC, PFS). All patients who have had surgery will be analyzed on an ITT for LRC, PFS, and survival.

Progression-Free Survival: Progression-Free Survival (PFS) is defined as the duration of time from start of treatment to time of objective disease progression or death.

Local Regional Control (LRC) will be defined as local and regional control of disease, censored for death.

Overall Survival (OAS) will be defined as alive at the time of analysis, this will be analyzed as for the entire trial, for all randomized patients and only for those patients randomized who received one dose of radiotherapy.

Post Recurrence LRC: Surveillance Patients who recur will be assessed for LRC post treatment for their initial recurrence

Post Recurrence PFS Surveillance Patients who recur will be assessed for PFS post treatment for their initial recurrence

Ultimate Disease Control will be defined as those patients who are alive and disease free at the time of analysis

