### **1.1 Primary Objectives**

- 1.1.1 To determine the rate of local regional control (LRC) at 5 years in patients with early and intermediate stage HPV related oropharynx cancer treated with surgery alone.
- 1.1.2 To determine the rate of progression free survival (PFS) at 5 years in patients with early and intermediate stage HPV related oropharynx cancer treated with surgery alone.
- 1.1.3 To determine overall survival (OS) at 5 years in patients with early and intermediate stage HPV related oropharynx cancer treated with surgery alone.
- 1.1.4 To determine the rate of local regional control (LRC) at 3 years in patients with HPV related oropharynx cancer treated with a de-intensified adjuvant protocol.
- 1.1.5 To determine the rate of progression free survival (PFS) at 3 years in patients with HPV related oropharynx cancer treated with a de-intensified adjuvant protocol.
- 1.1.6 To determine overall survival (OS) at 3 years in patients with HPV related oropharynx cancer treated with a de-intensified adjuvant protocol.
- 1.1.7 To determine the rate of PFS (Ultimate Disease Control – UDC) and of OAS after secondary therapy for patients treated with surgery only who have local regional relapse at 5 years
- 1.1.8 To determine the rate of PFS (UDC) and OAS after secondary therapy for patients who relapse with distant disease after surgery only
- 1.1.9 To quantify the quality of life of patients treated with this protocol at 3 years

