### **5.2 Salvage Protocol**

In the event of suspected disease recurrence in the surveillance group (Group I), appropriate imaging including PET/CT scan and biopsies will be performed. Biopsies will be evaluated for HPV16 and p16 expression and

CONFIDENTIAL

This document is confidential. Do not disclose or use except as authorized.

stored for further analysis. If there is solely a local regional recurrence, Surgical salvage will be offered to patients who have resectable limited disease defined as recurrent disease at the primary site or level 2 or 3 lymph nodes and <3 positive nodes on scan, followed by post-operative CRT as above for group 3 patients. For patients with limited recurrence deemed unresectable for reasons of organ preservation or ability to reasonably expect a complete surgical resection, definitive CRT with a total dose of 6600-7200 cgy and cisplatin as above will be performed.

For patients with extensive local regional disease defined as infiltrative, >2 positive nodes, nodal involvement of levels 4, 5 or N2c disease or those with metastatic disease, TPF chemotherapy will be given. After completion of 3 cycles of TPF, sites of initial disease will be treated with carboplatin to 5600 cGy as defined in the Quarterback trial. TPF will be given even if the metastases have been completely resected post TPF. CRT will be delivered to sites and watershed areas of metastatic disease that has been resected or is unresectable and there was no LR recurrence. For multiple metastases TPF and CRT may be withheld if in the opinion of the clinician the DM are too numerous and desminated to be safely or effectively treated.

Patients in Group II or Group III who fail with LR disease will be treated with best available therapy.

If a specific and highly effective therapy is identified during the conduct of the study that is an improvement over treatment with TPF and CRT as salvage, that therapy may be offered to the patients as a standard treatment, and will be added as an amendment in due course.

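### Post-recurrence PFS and OAS have no time origin and no rule for relapses left untreated or failing before salvage, so the natural reading overstates salvage success, chiefly for objective 1.1.8

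*Combined protocol and SAP*

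**What the plan says.** Section 11.1.1 defines two post-recurrence endpoints, both conditioned on treatment of the relapse. For PFS: "Post Recurrence PFS Surveillance Patients who recur will be assessed for PFS post treatment for their initial recurrence". For LRC: "Surveillance Patients who recur will be assessed for LRC post treatment for their initial recurrence". Neither has a start date or a rule for patients who receive no treatment.

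The objectives carry the same condition. Objective 1.1.8 reads: "To determine the rate of PFS (UDC) and OAS after secondary therapy for patients who relapse with distant disease after surgery only". Objective 1.1.7 uses parallel wording for local regional relapse. Both are listed as primary.

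Section 5.2 provides for relapses that go untreated: "For multiple metastases TPF and CRT may be withheld if in the opinion of the clinician the DM are too numerous".

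Three other statements in Section 11.1.1 bear on the reading:

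- General PFS "is defined as the duration of time from start of treatment to time of objective disease progression or death".
- UDC, which the objectives put in brackets after PFS, has no treatment condition: "Ultimate Disease Control will be defined as those patients who are alive and disease free at the time of analysis".
- The intention-to-treat sentence does not mention the post-recurrence endpoints: "All patients who have had surgery will be analyzed on an ITT for LRC, PFS, and survival".

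Sections 16.4 and 16.5 do not analyse the post-recurrence endpoints. Section 16.2 promises a posterior distribution for each sub-aim, but gives no denominator for the relapsed subset.

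**The concern.** Section 2.3 defends omitting radiotherapy partly on the expectation that delayed or salvage treatment will work well in these patients. Objectives 1.1.7 and 1.1.8 are where the trial tests that expectation. If a relapsed patient enters the estimate only by being treated, the trial answers whether treated relapses are controlled. It does not answer whether relapse after surgery alone can be controlled. The patients most likely to be missing have disseminated disease or deteriorate before salvage, and nearly all of them would be failures. Leaving them out can only raise the reported salvage rate. With no rule written down, the denominator would also be chosen after the outcomes are known.

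**Working it through.** The documents give no salvage control rate and no expected untreated share, so there is no planned figure to reproduce. The check has three parts.

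**1. Who counts under each reading of the text**

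| Relapsed Group I patient | Clock starts after salvage ends | Clock starts at start of salvage (general PFS clock carried over) | UDC as a status at analysis, over all who recur |
|---|---|---|---|
| Never treated | not counted | not counted | failure |
| Progresses or dies before salvage | not counted | not counted | failure, unless later disease free |
| Progresses or dies during salvage | not counted | failure | failure, unless later disease free |

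The wording of Section 11.1.1 and of the objectives points to one of the first two columns. The UDC definition allows the third. All three can be argued from the text, so the passages conflict on the denominator.

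**2. Size of the overstatement**

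Let s be the control rate among treated relapses, and f the share of all relapses that is untreated or fails before salvage. If the clock starts only after salvage, f also includes failures during salvage. None of the patients in f is controlled.

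- Treated-only rate = s
- All-relapse rate = s × (1 − f) + 0 × f = s(1 − f)
- Overstatement = s − s(1 − f) = s × f

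Both s and f are assumptions:

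| s | f | All-relapse rate | Overstatement |
|---|---|---|---|
| 50% | 10% | 45% | 5 points |
| 50% | 20% | 40% | 10 points |
| 50% | 30% | 35% | 15 points |
| 70% | 10% | 63% | 7 points |
| 70% | 20% | 56% | 14 points |
| 70% | 30% | 49% | 21 points |

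**3. How many patients this concerns**

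Section 16.2 plans 100 Group I patients and tabulates recurrence rates of .1 to .5, which is 10 to 50 relapses in total. Objectives 1.1.7 and 1.1.8 each take part of these. With a beta(1,1) prior and 70% observed control, the 95% credible interval is:

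- 10 relapses: 0.39 to 0.89
- 20 relapses: 0.48 to 0.85
- 50 relapses: 0.56 to 0.81

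One patient can move the result visibly. Seven controlled out of 10 relapses is 70%. If one of the three failures is dropped because that patient was never treated, the figure is 7/9 = 78%. Sampling error is large at these numbers, but it can go either way. This exclusion goes one way.

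**The case against.** The strongest reply is that no passage excludes anyone. Section 11.1.1 names the population as surveillance patients who recur, and the measure bracketed in the objectives, UDC, is a status with neither a clock nor a treatment condition. An untreated disseminated relapse can be counted there as a failure. This stands in part. A reader might infer that the plan lays down an exclusion, but the documents support only an exclusion implied by wording and omission. The objectives still place UDC after secondary therapy, so its definition does not settle the denominator.

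Three further limits stand in full:

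- A reader might infer that progression or death during salvage is always lost. That holds only if the clock starts after salvage. If the general PFS clock carries over, those failures count, and only failures before or without salvage are lost.
- A reader might take the withholding provision to affect both objectives. It is written for multiple metastases, so it bears on 1.1.8. For 1.1.7 the gap concerns patients who decline salvage or fail before it.
- Neither objective names LRC, and the general LRC definition is "will be defined as local and regional control of disease, censored for death". Counting death as a post-recurrence LRC failure would contradict it.

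It can also be said that outcome among treated relapses is a legitimate descriptive quantity. It is, if labelled as such. It does not answer the question raised in Section 2.3.

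**Conclusion.** The concern holds as a gap in definition. Two primary objectives rest on endpoints with no time origin and no rule for relapses that are untreated or fail before salvage. The natural reading omits those patients and biases the salvage estimate upward, chiefly for 1.1.8. The illustrated size is 5 to 21 points, resting on assumed values of s (50-70%) and f (10-30%); the documents fix neither.

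A reader might go further and infer that the trial's overall case for surgery alone is biased. The documents do not support that. The main hypothesis in Section 16.1 concerns 5-year OAS and UDC for surgery alone and is not limited to salvaged patients, and the intention-to-treat sentence covers all operated patients for LRC, PFS and survival. The bias is confined to the salvage objectives.

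**What to change.** In Section 11.1.1 and in the wording of objectives 1.1.7 and 1.1.8:

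- Start post-recurrence PFS and OAS at the date of first documented relapse.
- Include every Group I patient who relapses, whether or not salvage is given or completed.
- Count progression or death before, during or without salvage, and untreated persistent disease, as PFS/UDC failure.
- Keep the existing censoring of death for post-recurrence LRC.
- Report the treated-only figure as a labelled supplementary result.

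A change of wording is not quite enough. Section 6.2 lists relapse as a reason for removal from study, and the Study Design paragraph of Section 1.0 says patients taken off study are followed for survival. Progression after relapse may therefore go unrecorded. The protocol should state that disease status continues to be recorded after relapse.

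The cost is the revised text, some added data capture after relapse, and lower reported salvage rates. No change to salvage treatment or other clinical management is implied.
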